6.5 Neuroimaging

MR imaging will be carried out on the UK based children in the University of Bristol Clinical Research and Imaging Centre (CRIC). A clinical 3 Tesla Siemens scanner will be used.

Brain anatomy and function will be imaged using standard clinical protocols. Conventional high spatial resolution T1 and T2 sequences (0.75 mm x 0.75 mm x 3 mm) will be acquired to assess brain anatomy and possible chronic abnormalities in brain parenchyma. T1-images will be used to determine total and partial brain volumes using both manual and automated segmentation.

Diffusion Tensor Imaging will be used to evaluate white matter integrity and projections of major fibre structures. To this end Fractional Anisotropy and Tractography will be acquired using MRI techniques provided by Siemens.

Blood Oxygenation Level Dependent (BOLD) Functional MRI (fMRI) will be used as readout for functional imaging. BOLD fMRI will be acquired using a standard T2*-weighted multi-slice technique (spatial resolution 3 mm³ with whole brain coverage) in block-design experiments with one item from the verbal, spatial and pictorial reasoning clusters as a task in the British Ability Scales. The fMRI will be individualised to each child's abilities and tolerance.

Great care will be taken not to over-tire the child, using breaks, drinks and changes of activity to maintain interest. The total time in the MRI scanner room will be around 35 - 45 minutes, the MR data acquisition itself will take 20-30 minutes.

7. 7. STUDY PROCEDURES

7.1 Informed Consent

The DRIFT trial PI ([name]) and staff have remained in contact with families and have forwarded the published results of the DRIFT trial. The families were all informed of the future school age follow-up and all were supportive of this.

Participants will be identified from the DRIFT trial database, which includes the NHS number. The majority of the children remain outpatients of UHBristol and North Bristol (NBT) NHS trusts, or their parents have remained in contact with [name]. Tracing their up to date address and phone numbers will be simple using the patient administration systems for each trust.

Where children are no longer patients of UHBristol or NBT and their survival status, latest address and telephone number are unknown a search will be performed using the NHS Care Record Service using the child's name, date of birth and NHS number. This will provide the current address, current GP and also if the child is still alive. In cases where survival status is unknown the Office of National Statistics will be approached to see if a death has been registered. In cases where the current address is not known the GP practice where they are registered will be contacted for information, to avoid information being sent to inappropriate addresses.

Parents of children from the DRIFT trial will be sent a letter of invitation by post to offer them the opportunity to be in the follow up study. This will be followed up by a telephone call 7 days later from the Study Coordinator ([name]), whom they all met at 2 years. The parents will be given the option to not receive a telephone call or any further contact if they so wish. If the parents and children have indicated that they are interested in the study a full information sheet for the parent, and an appropriate information sheet for the child will be forwarded. The study coordinator will contact the parents by their preferred method of communication 7 days later. At this time the parents can ask questions, share any special needs to accommodate and indicate if their child would like to participate or not. If parents and their child agree to take part, full consent will be taken in person from the parent and assent will be requested from the child.

On the day of the study assessments and MRI full informed consent will be taken from the parent with assent from the child.

Consent will be sought for the research team to access all the children's health records, routinely collected data and educational outcomes for this study and for future research use (subject to appropriate ethical approval), as well as for linkage of these data in the long term.

Families will be reimbursed for their expenses in taking part. The children will be given a gift voucher (£20) as a small token of thanks for their participation.

It is not intended to give the families individual feedback on full analysis of the assessments and images. A picture of the brain scan will be given to the child and parents if they wish. A summary of relevant findings will be sent in a letter with an offer to discuss them more fully on the telephone or face-to-face.

7.2 Assessment Visit

Families will be invited to attend a study Assessment Day at CRIC. Where travel to Bristol will be too burdensome for the children assessments will be performed at home or school as preferred by their parents. We know of a minority of cases that have moved to other countries. Where parents have indicated that they wish to participate and it is not possible for the assessment team to travel those distances alternative arrangements will be made for a

local child development team to perform at least the cognitive assessment, which is the primary outcome measure for the study.

After informed consent has been obtained, parents will complete the Strengths and Difficulties questionnaire [16]. This will allow the researchers to appropriately plan the assessment visit to the level of the child's abilities.

7.3 Withdrawal from the Study

Parents are free to withdraw consent for their child to continue to participate in the study at any time. Data collected to that point will be retained.

7.4 Data Analysis

Analysis will be performed by intention to treat and hence primary outcome (cognitive score) will be assessed by comparing mean scores, and analysed using the Student t-test (unpaired). Developmental Quotient derived from age equivalent cognitive scores will be used as a continuous variable, derived from either the BAS III or BSID Bayley III scales.

For the secondary outcomes with continuous outcomes (eg Movement ABC), these will also be analysed using Students t-test, unless found in this population to not follow a normal distribution, in which case either a suitable transformations will be sought or a non-parametric approach considered.

For the binary secondary outcomes (eg functional motor impairment, Strengths and Difficulties, use of specialised health, rehabilitative or educational services) the Chi-Square or 2-tailed Fishers exact test will be used. Output from the clinical neuroimaging will be transformed into either binary (in the case of radiology reports) or continuous data (in the case of quantitative measures) and analysed as above.

Any sensitivity analyses will be performed using multivariate linear regression analysis to control for variables of interest. Co-variate variable selection will be performed a-priori for the models, and included if clinically felt to represent potentially important cofounders. To provide consistent reporting, it is anticipated that at least one sensitivity analysis will be performed: adjusting for the pre-randomisation co-variates used in the initial DRIFT trial report.

For all tests a conventional level of statistical significance at 5% will be used.

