5.1 Study Participants

Children previously enrolled in and randomised to the DRIFT trial in Bristol and Poland between 2003 and 2006.

Inclusion criteria of the DRIFT trial were:

- (1) IVH documented on ultrasound;
- (2) age no more than 28 days;
- (3) progressive dilation of the both lateral ventricles with each side:
 - (a) ventricular width 4 mm over the 97th centile;

(b) all of the following: anterior horn diagonal width 4 mm (1 mm over 97th centile), thalamo-occipital distance 26 mm (1 mm over 97th centile), and third ventricle width 3 mm (1 mm over 97th centile); or

(c) measurements above (a) or (b) on 1 side combined with obvious midline shift indicating a pressure effect.

Exclusion criteria were a prothrombin time of >20 seconds or accelerated partial thromboplastin time of >50 seconds or platelets <50000/mL.

The DRIFT study achieved a high level of loyalty from those recruited as 100% followup was obtained at 2 years with 97% of the survivors having the full Bayley Scales of Infant Development administered. All the families received a copy of the paper reporting the two year findings of the trial. The families with a child in the DRIFT trial will be invited to take part.

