5.2 Statistical Considerations

In total 74 children (54 from Bristol and 20 from Poland) were randomised to the DRIFT trial of which 66 survived. 16 children are available for assessment in Poland and 50 in Bristol. Based on a similar effect size documented with severe cognitive disability at 2 years of age a two group continuity corrected chi-square test with a 5% two-sided significance level will have 80% power to detect the difference in severe cognitive disability between a control group proportion of 59% and odds ratio of 0.17 (i.e. an intervention proportion of 19.7%) when the sample size in each group is 28. With 60 infants (30 in each group) we will have 97% power (with an alpha of 5%) to detect a mean cognitive difference of 1 standard deviation (commonly 15 points) between the DRIFT and control groups.

45 UK children will be assessed in Bristol, and 15 Polish children in Katowice, Poland, assuming a 90% follow-up rate. It is intended to recruit 45 Children (22 DRIFT, 23 Control) from the Bristol cohort and 15 (8 DRIFT, 7 Control) from the Poland cohort.

Funding is available for the study to be completed in the UK and in Poland. **This protocol describes the UK cohort only**. The Poland cohort will be completed under a separate protocol and in accordance with local governance and regulatory requirements.

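### The primary t-test is labelled intention to treat but can use only survivors assessed at school age, and the near-complete 2-year scores are not used to check selective non-return

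*Protocol*

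**What the plan says.** Section 7.4 of the protocol sets the population and the test in one sentence: "Analysis will be performed by intention to treat and hence primary outcome (cognitive score) will be assessed by comparing mean scores". The test is Student's unpaired t-test on the developmental quotient. The section gives no rule for a surviving child without a quotient. It says that any sensitivity analysis will be multivariate linear regression and expects at least one, adjusting for the pre-randomisation covariates of the first trial report.

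Section 5.2 gives the numbers: "In total 74 children (54 from Bristol and 20 from Poland) were randomised to the DRIFT trial of which 66 survived", and "45 UK children will be assessed in Bristol, and 15 Polish children in Katowice, Poland, assuming a 90% follow-up rate". Section 5.3 requires fresh parental consent and the child's assent, so a family that declines supplies no score. Section 7.3 keeps whatever was collected before a withdrawal.

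On the earlier assessment, section 5.1 reports that "100% followup was obtained at 2 years with 97% of the survivors having the full Bayley Scales of Infant Development administered". Section 7.4 gives these data no role.

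**The concern.** Intention to treat keeps every randomised child in the arm to which the child was allocated. It does not lead to a comparison of means among those who came back. Here the label sits on a test that leaves out living, randomised children whose families decline, or who withdraw before cognitive testing. Regression on pre-randomisation covariates does not bring them back, because a child without an outcome leaves that model too.

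Non-return could plausibly be selective. DRIFT involved ventricular catheters placed under anaesthesia (section 3.1.2), so parents can be presumed to know the arm. All families received the paper with the 2-year findings (section 5.1). The protocol itself expects travel to be harder for children with severe mobility or emotional problems (section 10.2). If low-scoring controls are lost more often, the comparison understates the DRIFT effect. If low-scoring DRIFT children are lost more often, it overstates it. An earlier cognitive score is held for nearly all of these children and could be used to check.

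**Working it through.** **The plan's own figures.**
- A difference of 1 SD with 30 per group and two-sided alpha of 5% gives 96.8% power (noncentral t) or 97.2% (normal approximation). The stated 97% reproduces.
- An odds ratio of 0.17 on 59% gives odds 0.17 × 0.59/0.41 = 0.245, so a proportion of 19.7%. The continuity-corrected sample size is 28 per group, as stated.

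**Expected loss.**
- Bristol 45/50 = 90%; Poland 15/16 = 94%; overall 60/66 = 91%. Missing: 66 − 60 = 6, or 9%.
- Planned assessed per arm: 22 + 8 = 30 DRIFT and 23 + 7 = 30 control.
- Full 2-year Bayley: 0.97 × 66 = 64.

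**Assumptions (not in the protocol).** 33 survivors per arm; SD 25; true difference 18 points; correlation r of 0.6, 0.7 or 0.8 between the 2-year and school-age scores. Non-returners are drawn at random from the lower 19 of 33 2-year scores in their arm (0.59 × 33 = 19.5, the control proportion with severe cognitive disability at 2 years).

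**Formula.** If m of n children are lost from a pool whose mean 2-year score lies d SDs below the arm mean, the mean of those assessed rises by m/(n − m) × d × r × SD. For the lower 19/33 = 0.576 of a normal distribution, d = 0.392/0.576 = 0.68, so d × SD = 17.0 points.

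| Low scorers lost (control/DRIFT) | Net shift in the difference | Expected difference, r = 0.6 to 0.8 | Simulated (5,000 runs each) |
|---|---|---|---|
| 3/3 | 0 | 18.0 | 18.0 to 18.1 |
| 4/2 | −(4/29 − 2/31) × 17.0 × r = −1.25r | 17.3 to 17.0 | 16.9 to 17.4 |
| 6/0 | −(6/27) × 17.0 × r = −3.78r | 15.7 to 15.0 | 15.2 to 15.7 |
| 0/6 | +3.78r | 20.3 to 21.0 | 20.4 to 20.8 |

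The standard error of the difference is about 25 × √(2/30) = 6.5 points. Regression imputation from the 2-year score within arm gave 17.9 to 18.2 in all four patterns, with a standard error of 6.2 to 6.5, the same as without imputation.

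**Second set of assumptions.** With the protocol's SD of 15, all six lost from the 12 lowest control scores, and r of 0.5 to 0.85 (4,000 runs each):
- with a true difference of 15 points, the mean difference falls to between 13.3 and 12.2, and power from 97% to between 92% and 88%;
- with no true difference, the bias is 1.7 to 2.8 points against DRIFT, and the rejection rate is 6.8% to 10.9% instead of 5%;
- losing three low scorers in each arm leaves the bias near zero and the rejection rate near 5%.

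**The case against.** Methods for missing scores are usually left to the statistical analysis plan, which is not shown. Section 7.4 neither orders deletion nor rules out imputation, and the one sensitivity analysis it names is a minimum. So silence alone is no fault. What remains is what the section does state: an intention-to-treat label on a test of returners, and a form of sensitivity analysis that cannot address non-return.

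The protocol also works to limit selective loss. It offers home or school visits and local teams abroad (sections 7.2 and 10.2), tracing through NHS records (section 7.1), and the Bayley III for children below the BAS III floor (section 6.1). It reports that families supported the follow-up. This makes large selective loss less likely, but it does not recover families who decline.

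A reader might infer more than the documents support:
- **That withdrawal removes a child.** Under section 7.3, a child withdrawn after cognitive testing keeps the score.
- **That a 2-year Bayley score exists for every child.** Follow-up was complete, but the full Bayley covers 97% of survivors.
- **That the result will be materially biased.** The planned 30 assessed per arm would be a 3/3 loss if survivors were 33 per arm, and equal selection then cancels. Losing six severely disabled controls would turn 59% into (0.59 × 33 − 6)/27 = 50%, but that needs every non-returner to be severe and in one arm.
- **That imputation is shown to remove the bias.** In the simulation, non-return was generated from the same 2-year score that was used to impute, so recovery was built in. Sections 3.1.1 and 3.1.2 themselves call 2-year cognitive testing limited.

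**Conclusion.** The point holds as one of labelling plus a missing check. As section 7.4 stands, the primary comparison covers assessed survivors only, the regressions it describes drop the same children, and 2-year data on nearly all of them have no role.

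The likely bias is modest: about zero with similar losses in both arms, about 1 point for a 4/2 split of low scorers, and 2 to 3 points if all six are lost from one arm. Against a standard error of about 6.5 points, even the extreme case is less than half a standard error. These sizes rest on assumed survivors per arm, SD, correlation and selection pattern, none of which the protocol gives. The direction could be either way.

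The documents do not show that non-return will be selective, or that the planned t-test is invalid. The point concerns living children who do not return. The eight deaths (74 − 66) are a separate matter.

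**What to change.** In section 7.4:

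1. Describe the t-test as a comparison of surviving children assessed at school age, by allocated arm, in place of the present intention-to-treat wording.
2. Add a sensitivity analysis that multiply imputes the school-age developmental quotient and severe-disability status, separately by arm, from the 2-year Bayley score and the pre-randomisation covariates. Apply it to children confirmed alive at school age without a score, not to a fixed 66, because section 7.1 allows that survival status may be unknown for some.
3. Use the 2-year score only as an auxiliary variable for imputation. It is measured after randomisation, and as a covariate in the treatment model it would absorb part of the effect.
4. Tabulate 2-year severe cognitive disability by arm for returners and non-returners.
5. Add a simple missing-not-at-random check that shifts the imputed scores over a stated range. With 3 of 33 imputed, a 15-point shift moves that arm's mean by 3/33 × 15 = 1.4 points; with 6 of 33, by 2.7.

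Section 5.2 says this protocol describes the UK cohort only, so the wording should be matched in the Polish protocol if the cohorts are analysed together.

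The cost is a change of wording and a little extra analysis on data already held. The imputation assumes that non-return is explained by the 2-year score, the covariates and the arm, which is why step 5 is needed.

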4. AIMS AND OBJECTIVES

Our primary hypothesis is that neurosurgical drainage, irrigation, and fibrinolytic therapy (DRIFT), which aims to lower pressure, distortion, free iron, and cytokines, will reduce severe cognitive disability in children assessed at school age.

Our secondary hypotheses are that DRIFT will improve:

- (a) cerebral visual dysfunction
- (b) sensorimotor ability
- (c) functional status
- (d) emotional/behavioural difficulties
- (e) preference based measures of health related quality of life
- (f) and reduce the health, social care and broader societal costs at age 11.

The aims of this study:

- 1) To compare cognitive function, visual function, sensorimotor ability and emotional wellbeing, between the two treatment groups in the DRIFT trial at school age.
- 2) To quantify functional status and use of community and specialist health and educational services.
- 3) To estimate the economic cost and outcomes of the DRIFT intervention by age 11, and model long-term costs and outcomes.
- 4) To quantify degree of ventricular dilatation and neurosurgical sequelae in the two treatment groups by clinical neuroimaging.

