4.1 Primary Outcome

Severe cognitive disability at school age.

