6.1 Cognitive Assessments

Assessment will be undertaken by child psychologists.

Cognitive testing in this group of children needs to use a method with a wide spread of abilities as some of the study children have very significant disabilities (Cognitive score below 55). The British Ability Scales (BAS III) comprise 21 short tests, each measuring particular types of knowledge, thinking and/or skills (Elliott and Smith. GL Assessment; London. 2012). The final type of score is "age equivalent". This is the age at which the score achieved by the child was average. The BAS III has a basal threshold at a developmental age of 3 years. In the event that children do not attain the basal scoring threshold of the BAS III, the cognitive and language scales from the Bayley Scales of Infant and Toddler Development III (BSID III) (Bayley N. Harcourt Assessment: San Antonio; 2006) will be administered. This test also yields Developmental Age Equivalent score from 1 month to 3 years. In order to compare scores in all children, developmental age scores will be converted into a developmental quotient score: [developmental age equivalent score \div biological age at assessment x 100] for each child. This allows severely delayed children to have a cognitive score rather than being labelled as "untestable".[14] The final cognitive score for children of all abilities will therefore be a cognitive developmental quotient and a continuous variable.

The BAS_III and BSID III will be adapted for use in Polish speaking children.

The individual scales for BASIII are:

- Block building
- Copying
- Early number concepts
- Matching letter-like forms
- Matrices
- Naming Vocabulary
- Number Skills
- Pattern Construction
- Picture Construction
- Picture Similarities
- Quantitative Reasoning
- Recall of Designs
- Recall of Digits Backwards
- Recall of objects

- Recognition of pictures
- Speed of information processing
- Spelling
- Verbal Comprehension
- Verbal Similarities
- Word definitions
- Word reading

The individual scales for BSID III are:

- Cognitive Scale
- Language Scale (receptive and expressive language)

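### The declared primary outcome is binary (severe cognitive disability), but section 7.4 tests a continuous cognitive score as primary, so the declared endpoint has no primary test

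*Protocol*

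**What the plan says.** **Binary outcome as primary.** The primary endpoint in the synopsis and the primary outcome in section 4.1 are the same: "Severe cognitive disability at school age". The primary hypothesis in section 4 is that DRIFT "will reduce severe cognitive disability in children assessed at school age". Section 5.2 leads with "80% power to detect the difference in severe cognitive disability", using a continuity-corrected chi-square test, a control proportion of 59%, an odds ratio of 0.17 and 28 children per group.

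**Continuous outcome as primary.** Section 7.4 states: "primary outcome (cognitive score) will be assessed by comparing mean scores, and analysed using the Student t-test (unpaired". It goes on: "Developmental Quotient derived from age equivalent cognitive scores will be used as a continuous variable". Section 6.1 agrees that the final score "will therefore be a cognitive developmental quotient and a continuous variable". Section 5.2 adds a second power figure, 97% with 30 per group for a mean difference of 1 SD.

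**Where binary tests are assigned.** Section 7.4 reads "For the binary secondary outcomes (eg functional motor impairment, Strengths and Difficulties, use of specialised health, rehabilitative or educational services) the Chi-Square" or Fisher's exact test. No binary primary outcome is mentioned there.

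**Neutral wording.** Section 7.2 refers to "at least the cognitive assessment, which is the primary outcome measure for the study", which fits either version.

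**What counts as severe.** Section 3.1.2 gives the rule used at 2 years, a Bayley mental development index 3 SD below the mean. Section 6.1 mentions a cognitive score below 55 when describing how disabled some of the children are. Neither is stated as the definition of the school-age endpoint.

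**The concern.** A proportion with severe disability and a mean developmental quotient (DQ) are different estimands. A shift in the mean does not show that fewer children fall below a severe threshold, and a change in that proportion can occur with little change in the mean. The hypothesis and the declared outcome concern the proportion. The primary analysis concerns the mean.

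Two things are at stake. The result presented as primary would not answer the stated primary question. And if the two analyses disagree, the Protocol supports calling either one primary, depending on which section is cited. A separate statistical analysis plan cannot remove this, because choosing either version would contradict part of the Protocol.

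**Working it through.** **1. The plan's binary figure (section 5.2).** Inputs: control proportion p1 = 0.59, odds ratio 0.17, two-sided 5%, 80% power.

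- Control odds: 0.59/0.41 = 1.439. Intervention odds: 1.439 × 0.17 = 0.2446. So p2 = 0.2446/1.2446 = 0.1966 (stated as 19.7%).
- Difference d = 0.3934; average proportion p̄ = 0.3933.
- Uncorrected n = [1.96√(2p̄(1−p̄)) + 0.8416√(p1(1−p1)+p2(1−p2))]² / d² = (1.354 + 0.532)² / 0.1548 = 22.98 per group.
- With continuity correction: (22.98/4)·[1 + √(1 + 4/(22.98 × 0.3934))]² = 27.8, so 28 per group, as stated.

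**2. The plan's continuous figure (section 5.2).** Standardised difference 1, n = 30 per group: power = Φ(√(30/2) − 1.96) = Φ(3.873 − 1.960) = 97.2%. The noncentral t gives 96.8%. Stated: 97%.

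Both calculations are right, but they serve two different endpoints, and section 5.2 does not say which one governs.

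**3. How far the two analyses can diverge.** The Protocol gives no school-age DQ distribution, so the following is assumed: normal scores, equal SD in both arms, 30 per arm, and a cut-off set so that 59% of controls are severe. The SD in points cancels; only the standardised shift matters. For an intervention proportion p2 the shift is Φ⁻¹(0.59) − Φ⁻¹(p2):

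- 59% vs 19.7% (design effect, section 5.2): 0.228 + 0.852 = 1.08 SD.
- 59% vs 31% (crude 2-year rates, section 3.1.2): 0.228 + 0.496 = 0.72 SD.

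Simulation of 40,000 trials per scenario, each test at two-sided 5%:

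| True proportions | t-test significant | Corrected chi-square significant | Verdicts differ | Only t-test significant | Only chi-square significant |
|---|---|---|---|---|---|
| 59% vs 19.7% | 98% | 84% | 15% | 14.7% | 0.1% |
| 59% vs 31% | 79% | 50% | 32% | 30.5% | 1.2% |

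With an uncorrected chi-square, the verdicts differ in 9% and 24% of trials respectively.

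**4. Type I error if either result could be called primary.** Under no effect (59% in both arms), at least one test is significant in about 6% of trials with the corrected chi-square and about 8% with the uncorrected one. Two independent tests would give 1 − 0.95² = 9.75%. The figure here is lower because the tests are correlated and the corrected test is conservative (2.6% on its own).

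**The case against.** The strongest reply is that section 7.4, read alone, is clear: it labels one outcome primary and fixes one test for it, an unpaired t-test on DQ at 5%. Section 6.1 builds the continuous score deliberately so that very disabled children are not lost as untestable, and section 5.2 gives it ample power. That stands. A reader might infer that the primary hypothesis has no decision rule at all. The documents do not support that, because there is a rule; it is attached to a different variable from the one declared.

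A reader might also infer serious type I error inflation. The excess is about 1 percentage point with the corrected test named in section 5.2, and about 3 points with an uncorrected one. Nothing in the Protocol says that the more favourable result would be chosen.

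It might be said that severe disability has no threshold anywhere. That goes too far: on a scale with SD 15 and an assumed mean of 100, the score below 55 in section 6.1 equals 3 SD below the mean, in line with the 2-year rule. But section 6.1 uses it to describe the children, not to define the endpoint.

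Finally, the 32% disagreement belongs to the crude 2-year rates, not to the effect on which the trial was powered. There the figure is 15%.

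**Conclusion.** The point holds as a contradiction within the Protocol. The declared primary endpoint, on which the first power statement rests, has no primary analysis, and the analysis called primary does not match the hypothesis. No other section resolves this, and the documents do not settle which outcome was intended.

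In size, the significance verdict would depend on the section cited in about 15% of trials at the design effect and about 32% at the crude 2-year rates, almost always because the t-test alone is significant. These figures rest on assumed normal scores with equal SDs, 30 assessed children per arm and 59% of controls below the cut-off; a skewed DQ distribution would change them. The contradiction itself needs no assumption. The sample size arithmetic is not in error.

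**What to change.** Before any comparison by arm, the sponsor should choose one primary outcome and use it in the synopsis and sections 4, 4.1, 5.2 and 7.4. Either choice is open.

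- **If binary:** state the school-age DQ cut-off for severe cognitive disability, enter its test in section 7.4 as the primary analysis, keep the 28-per-group calculation as the primary power statement, and make mean DQ secondary.
- **If continuous:** rewrite the synopsis endpoint, primary hypothesis and section 4.1 as mean DQ, make the 1 SD / 97% calculation the primary power statement, and list severe cognitive disability, with a defined cut-off, as a secondary outcome.

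The cost is a protocol amendment, to the analysis in the first case and to the declared endpoint and hypothesis in the second. The second is a substantive change and should be documented as made before results by arm were known. The same cognitive assessments serve both options, so no extra data collection is needed.
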